Population	Pregnant women exposed to any glucocorticoid or corticosteroid or steroids in early pregnancy or first trimester of pregnancy irrespective of mode of administration identified from articles published up to 25 June 2018 by pre-specified inclusion and exclusion criteria				
Variables	 Exposure definition First trimester exposure Early pregnancy Outcomes definition Oral clefts Cleft lip with or without palate Cleft palate Covariate definition Potency of glucocorticosteroids Route of administration of glucocorticosteroids 				
Data sources	 Embase and Medline via Ovid®, Cochrane database, Google Scholar has been used for data collection All records retrieved from the literature searches have been screened for relevancy based on eligibility criteria (inclusion/exclusion). Relevant back references from the shortlisted studies have also been reviewed. 				
Study size	18 observational studies have been selected for meta-analysis by predefined eligibility criteria in a previously conducted SLR.				
Data analysis	 Direct treatment comparison: Any glucocorticoid or corticosteroid or steroids use irrespective of mode of administration vs. no use of glucocorticosteroids Model: Fixed effect model Measure of relative effect: For the dichotomous outcomes will be assessed by Odds ratio (OR) Inverse variance method Effect size are assessed by Odds ratio (OR) as it is a rare outcome Publication bias: Using funnel plot, Egger's test, Galbraith plot Sensitivity analysis Sub-group analyses Route of administration: Types of orofacial cleft Potency of glucocorticoid 				

	 Data will be analysed by using the metafor package in R software version 3.5.1 The results of the outcomes will be described as eman with 95% credibility intervals (CI) and presented as Forrest plots 			
Milestones	Start of data collection (SLR): 12 June 2018			
	End of data collection (SLR): 25 June 2018			
	Final report (SLR): 9 July 2018			
	Meta-analysis protocol: 09 November 2018			
	Statistical analysis plan: 10 September 2018			
	Meta-analysis report: November 2018			

5. Amendments

Not applicable.

6. Milestones

Table 1 presents the planned milestones for the project. These milestones are based on a timely review and approval of the project. Administrative changes to milestones due to delays in study preparation, data release and analysis do not require amendments to the protocol.

Table 1: Milestones

Milestone	Planned date
Start of data collection (SLR)	12 June 2018

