9.2 Setting

Pregnant women exposed to any glucocorticoid or corticosteroid or steroids in early pregnancy or first trimester of pregnancy irrespective of mode of administration identified through a systematic review of articles published up to 25 June 2018 by pre-specified inclusion and exclusion criteria (see section 4 of SLR in see Appendix 1). In total 18 observational studies have been selected for this meta-analysis with sample size for individual studies ranging from 106 to 832,636 patients.

- Source: Embase and Medline via Ovid®, Cochrane database, Google Scholar
- *Population sampling strategy:* All records retrieved from the literature searches were screened for relevancy based on eligibility criteria (inclusion/exclusion). The results were initially screened by title and abstract, and the shortlisted results were further screened on full text. Relevant back references from the shortlisted studies have also been reviewed.

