9.5 Study size / Recall

18 observational studies were selected for meta-analysis by predefined eligibility criteria. For details, please refer to section 4 of systematic literature review report provided in Appendix 1.

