9.7 Data analysis

- Direct treatment comparison: Any glucocorticoid or corticosteroid or steroids use irrespective of mode of administration vs. no use of glucocorticosteroids
- Model: Fixed effect model will be used. We assume that the underlying effect size is the same across the studies. The differences in observed effects are only due to random error or sampling error within the studies. The observed effects mainly depend on the sample size and weighted average mean might give a precise estimation of the overall effect. However, any deviation from this assumption will be discussed.
- Measure of relative effect: For the dichotomous outcomes will be assessed by Odds ratio (OR). Given that the event of our interest is a rare outcome, we assume relative risk (RR) equivalent to OR.
- Inverse variance method: Studies with less variance or standard deviation are given more weight. The variance of weighted average can be minimized through this method and hence inverse variance method will be used to assess the direct treatment effect
- Effect size is assessed by Odds ratio (OR) as it is a rare outcome
- Publication bias: Reporting or publication bias will be assessed by using the funnel plot (symmetry or asymmetry) and it again confirmed by using the Egger's test (in case of asymmetry funnel plot). Further, any outliers in the effect size will be determined by Galbraith plot
- Sensitivity analysis: In order to know the robustness of the findings, sensitivity analysis will be performed with and without outlier studies so that any uncertainty can be determined. This will be done only in case of high level of heterogeneity observed. However, plausible reasons for high heterogeneity (unexplained variation) will be discussed in the MAR
- Sub-group analyses will be performed for
 - Route of administration:
 - Topical
 - Systemic
 - Any other form of use
 - Types of orofacial cleft
 - Cleft lip (CP)
 - Cleft lip with or without palate (CLP)
 - Cleft palate (CP)
 - Orofacial cleft (OC)
 - Potency of glucocorticoid
 - Mild
 - Moderate
 - Potent
 - Very potent
- 95% credibility intervals will be used as a measure for the expression of the difference (overlap / no overlap with 1 for OR)
- Data will be analysed by using the metafor package in R software version 3.5.1

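### The Galbraith plot flags studies by standardised deviation, not by effect size, so under high heterogeneity the planned analysis without outliers tends to trim the precise studies and is a weak robustness check

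*Protocol*

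**What the plan says.** Section 9.7 of the protocol fixes four things that act together.

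- **Model:** "Fixed effect model will be used. We assume that the underlying effect size is the same across the studies". Weights are inverse variance: "Studies with less variance or standard deviation are given more weight".
- **Outlier rule:** "any outliers in the effect size will be determined by Galbraith plot". No other outlier tool is named.
- **Use of the rule:** "sensitivity analysis will be performed with and without outlier studies so that any uncertainty can be determined".
- **Trigger:** "This will be done only in case of high level of heterogeneity observed".

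This is the only sensitivity analysis described in 9.7. The data analysis row of the Abstract (section 4) lists the plot among the publication-bias tools: "Using funnel plot, Egger's test, Galbraith plot". Section 9.5 gives the number of studies: "18 observational studies were selected for meta-analysis by predefined eligibility criteria". Section 9.2 gives the "sample size for individual studies ranging from 106 to 832,636 patients". Section 7 names heterogeneity among the 18 publications as the reason for doing the meta-analysis, so the trigger may well be met.

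**The concern.** A study falls outside a Galbraith band when its log odds ratio differs from the pooled log odds ratio by more than about two of its own SEs. That is a standardised residual, not a measure of how extreme the effect is. The two rank studies differently whenever precision varies.

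Without between-study variance, every study has about the same small chance of being flagged and the rule is coherent. The exclusion, however, is planned only when heterogeneity is high. True effects then differ between studies, and a precise study is outside the band merely because its SE is small compared with the ordinary spread of effects.

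What is at stake is the reading of the one planned robustness check. It can remove several informative studies together, and what remains agrees well because the disagreeing precise studies have been taken out. A reader could mistake that agreement for reassurance.

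**Working it through.** The plan gives no figure to reproduce, and no study-level odds ratios or SEs.

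**Inputs.** From the protocol: 18 studies, fixed-effect inverse-variance line, exclusion only under high heterogeneity. Assumed: SEs of the log odds ratio, between-study SD τ, a band of 1.96 or 2, and I² above 50% as the meaning of high heterogeneity.

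**1. What the band measures.** A study is flagged if |ln OR − ln pooled OR| / SE > 2. With an illustrative pooled OR of 1.2:

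- OR 6, SE 0.85: ln(6/1.2)/0.85 = 1.89, not flagged.
- OR 3, SE 0.46: ln(3/1.2)/0.46 = 1.99, not flagged.
- OR 1.5, SE 0.10: ln(1.5/1.2)/0.10 = 2.23, flagged.

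The least extreme of the three effects is the one called an outlier. With a band of 1.96, the factor from the pooled OR needed to be flagged is exp(1.96 × SE): 1.22 at SE 0.1, 2.66 at SE 0.5 and 7.1 at SE 1.0.

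**2. Chance of a flag, line treated as known.** P = 2Φ(−1.96 × SE / √(SE² + τ²)).

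- τ = 0: 0.05 at every SE.
- τ = 0.3, SE 0.1: √(0.01 + 0.09) = 0.316, so P = 2Φ(−0.62) = 0.54.
- τ = 0.3, SE 1.0: √(1 + 0.09) = 1.044, so P = 2Φ(−1.88) = 0.06.

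**3. Simulation with the line re-estimated.** 18 studies, SEs log-spaced from 0.1 to 1.0, band of 2, runs with I² above 50%:

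| τ | Most precise third flagged | Least precise third flagged | Weight removed |
|---|---|---|---|
| 0.2 | 36% | 8% | 35% |
| 0.3 | 43% | 8% | 41% |
| 0.5 | 57% | 12% | 54% |

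Repeat runs differ by about one percentage point. At τ = 0.3 about 4 of the 18 studies are removed. Median I² among the remaining studies is about 0% to 5% across these values of τ.

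**4. Other SE layouts, τ = 0.3, band 1.96, all runs.** Chance of a flag for the most precise and the least precise study:

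| SE layout | Most precise | Least precise |
|---|---|---|
| Graded 0.08–1.0 | 0.52 | 0.06 |
| Graded 0.15–0.8 | 0.31 | 0.07 |
| Three large (0.08–0.12), rest 0.25–1.0 | 0.47 | 0.06 |
| One dominant (0.05, 75% of weight), rest 0.2–1.0 | 0.24 | 0.07 |

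Mean weight removed is 23% to 43%. The study farthest from the pooled log odds ratio is flagged in 44% to 55% of runs. Over τ from 0.2 to 0.5, the most precise study is flagged in 9% to 70% of runs.

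**5. What the plot does well.** If one study deviates by a factor of 3 and the others are homogeneous, it is flagged with probability 1.00 at SE 0.2, 0.96 at 0.3, 0.59 at 0.5 and 0.20 at 1.0.

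**The case against.** The strongest reply is that, under the protocol's own estimator, the studies that the plot misses hardly matter. In the layout of step 3 the weights 1/SE² sum to about 418. A study with OR 3 and SE 0.46 has weight 4.7, or 1.1% of the total, and leaving it out moves a pooled OR of 1.20 to 1.19. A study with OR 1.5 and SE 0.10 has weight 100, or 24%, and leaving it out moves 1.20 to 1.12. In simulation at τ = 0.3 with I² above 50%, the single most influential study is flagged in 95% of runs (92% at τ = 0.2, 98% at 0.5). The least precise third holds 3.1% of the weight before trimming and about 5% after. This stands, and it rules out saying that trimming hands the answer to the weak studies.

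It does not rescue the rule. Flagging the most influential study is useful, but the plan then removes every flagged study together, so the effect of any one of them cannot be read off.

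Three further replies also stand. The all-study result is reported alongside. Section 9.7 promises to discuss departures from the common-effect assumption and reasons for high heterogeneity. The band is not stated, and a cut-off may properly be in the SAP, which exists but is not shown, so its absence is not held against the protocol.

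It can also be said that the root cause is the fixed-effect choice, since the rule is coherent when τ = 0. That is true, but the exclusion is reserved for the case where τ = 0 is in doubt.

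**Conclusion.** The point holds in a limited form. The Galbraith plot does not identify outliers by effect size, and the only planned robustness check relies on it precisely when flagging depends most on precision. Under the stated assumptions, about 36% to 57% of the most precise third is flagged, 35% to 54% of the weight is lost, and the trimmed set looks nearly homogeneous. The direction was the same in every layout tried. The size rests on assumed SEs, τ, band and I² threshold.

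Three stronger readings are tempting and not supported:

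- **That the plot cannot find outliers.** It finds a reasonably precise aberrant study almost always; what it lacks is sensitivity for imprecise ones.
- **That it discards the largest studies.** This is a tendency (9% to 70% for the most precise study), weaker when one study dominates and pulls the line towards itself. The size range in section 9.2 also does not give precision, which for a rare outcome depends on exposed cases.
- **That it shields the 3- to 6-fold reports in section 7.** The protocol does not say that those reports are imprecise; with small SEs they would be flagged.

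The primary estimate is unaffected. The change is worth making because the check would be weak, and possibly misleading, when it is needed.

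**What to change.** In section 9.7, replace the outlier sentence and the with/without rule by text to this effect: The pooled odds ratio will be shown with each of the 18 studies left out in turn. Outlying studies will be identified from deleted (externally standardised) residuals of a model that includes between-study variance, and influential studies from Cook's distance. The Galbraith plot will be shown only as a display of heterogeneity.

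The model with between-study variance serves here as a diagnostic and does not by itself change the primary analysis. In the Abstract, move the Galbraith plot out of the publication-bias list so that it matches section 9.7.

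The cost is a change of wording in two places, a few more lines of R in the metafor package already named, and one more table or plot. No new data are needed.

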6.4	Does the protocol describe specific outcomes relevant for Health Technology Assessment? (e.g. HRQoL, QALYs, DALYS, health care services utilisation, burden of disease or treatment, compliance, disease management)		\boxtimes		

The study is a meta-analysis of literature. The outcome investigated is orofacial cleft in the offspring of mother exposed to corticosteroids during the first trimester of pregnancy.

Sect	ion 7: Bias	Yes	No	N/A	Section Number
7.1	Does the protocol address ways to measure confounding? (e.g. confounding by indication)		\boxtimes		
7.2	Does the protocol address selection bias? (e.g. healthy user/adherer bias)		\boxtimes		
7.3	Does the protocol address information bias? (e.g. misclassification of exposure and outcomes, time-related bias)		\boxtimes		

Comments:

Reporting or publication bias will be assessed by using the funnel plot (symmetry or asymmetry) and it again confirmed by using the Egger's test (in case of asymmetry funnel plot). Further, any outliers in the effect size will be determined by Galbraith plot

Sect	ion 8: Effect measure modification	Yes	No	N/A	Section Number
8.1	Does the protocol address effect modifiers? (e.g. collection of data on known effect modifiers, sub-group analyses, anticipated direction of effect)	\boxtimes			9.7

Comments:

Sect	ion 9: Data sources	Yes	No	N/A	Section Number
9.1	Does the protocol describe the data source(s) used in the study for the ascertainment of:				
	9.1.1 Exposure? (e.g. pharmacy dispensing, general practice prescribing, claims data, self-report, face-to-face interview)		\boxtimes		
	9.1.2 Outcomes? (e.g. clinical records, laboratory markers or values, claims data, self-report, patient interview including scales and questionnaires, vital statistics)		\boxtimes		
	9.1.3 Covariates and other characteristics?	\square			9.3.3
9.2	Does the protocol describe the information available from the data source(s) on:				
	9.2.1 Exposure? (e.g. date of dispensing, drug quantity, dose, number of days of supply prescription, daily dosage, prescriber)		\boxtimes		
	9.2.2 Outcomes? (e.g. date of occurrence, multiple event, severity measures related to event)		\boxtimes		

Sect	ion 9: Data sources	Yes	No	N/A	Section Number
	9.2.3 Covariates and other characteristics? (e.g. age, sex, clinical and drug use history, co-morbidity, co-medications, lifestyle)		\boxtimes		
9.3	Is a coding system described for:				

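### The only named sensitivity analysis waits for undefined high heterogeneity and excludes studies by effect size, and Egger's test waits for a funnel plot judged asymmetric by eye

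*Protocol*

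**What the plan says.** Section 9.7 of the protocol pools by inverse variance under a fixed-effect model: "We assume that the underlying effect size is the same across the studies". Section 9.5 gives the number of studies: "18 observational studies were selected for meta-analysis by predefined eligibility criteria".

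Section 9.7 then sets out the checks:

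- **Funnel plot:** planned without a condition.
- **Egger's test:** conditional on the plot, "it again confirmed by using the Egger's test (in case of asymmetry funnel plot"). The ENCePP checklist in Annex 2 (Section 7, Bias) repeats this condition.
- **Galbraith plot:** planned without a condition, and used to select on the result: "any outliers in the effect size will be determined by Galbraith plot".
- **Sensitivity analysis:** "sensitivity analysis will be performed with and without outlier studies so that any uncertainty can be determined". Its stated purpose is to learn how robust the findings are. It carries the restriction "This will be done only in case of high level of heterogeneity observed".

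The protocol gives no statistic or threshold for high heterogeneity. Subgroup analyses by route, cleft type and potency are unconditional. Section 9.8 plans a Newcastle-Ottawa appraisal but links it to no sensitivity analysis.

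**The concern.** A robustness check that runs only after a data-dependent trigger says nothing about robustness when the trigger does not fire. Here the trigger is also undefined, so the decision can be taken after the results are seen.

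The assumption most in need of testing is a single common effect. Section 7 justifies the meta-analysis by the heterogeneous findings of the 18 publications. Section 9.9 lists confounding, a wide dosage range and differences in skin absorption as possible influences on the results. If heterogeneity is called moderate, the fixed-effect interval stands with no sensitivity analysis beside it.

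If the trigger does fire, the one analysis on offer excludes studies because of their results, not their design or quality. It can show whether the estimate leans on extreme studies. It cannot test robustness to the model, study design, confounding or quality.

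For publication bias, which section 9.9 names as a limitation, a reading by eye decides whether the formal test exists. The study answers a regulator's safety question, so an interval that is too narrow matters whichever way the estimate falls.

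**Working it through.** The protocol gives no power figure, heterogeneity cut-off or study-level precision for this point, so there is no stated figure to reproduce. The check is the text above plus an illustration.

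**Inputs.** From the protocol: k = 18 studies, inverse-variance fixed effect, outliers by effect size on a Galbraith plot. Assumed: true OR 1.2; standard error (SE) of each log OR uniform on 0.1–0.6; between-study SD τ from 0 to 0.5; outlier limit 1.96; I² as the heterogeneity statistic, with high meaning above 50% or above 75%. There were 5,000 runs per scenario.

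**Formulas.** wᵢ = 1/SEᵢ²; m = Σwᵢyᵢ/Σwᵢ; SE(m) = (Σwᵢ)^(−1/2); Q = Σwᵢ(yᵢ − m)²; I² = max(0, (Q − 17)/Q). Study i is excluded if |yᵢ − m|/SEᵢ > 1.96. Coverage is the share of runs in which m ± 1.96·SE(m) contains the mean true effect.

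| τ | Mean I² | I² > 50% | I² > 75% | Coverage, all 18 | Coverage where I² ≤ 50% | Studies excluded | Mean I² after | Coverage after |
|---|---|---|---|---|---|---|---|---|
| 0 | 9% | 1% | 0% | 95% | 95% | 0.8 | 2% | 94% |
| 0.1 | 15% | 3% | 0% | 90% | 90% | 1.1 | 3% | 88% |
| 0.2 | 32% | 23% | 0.3% | 78% | 80% | 2.0 | 5% | 79% |
| 0.3 | 51% | 59% | 8% | 67% | 72% | 3.2 | 7% | 73% |
| 0.5 | 74% | 94% | 58% | 46% | 53% | 5.6 | 12% | 60% |

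**The trigger.** At τ = 0.2, I² is 50% or less in about 100 − 23 = 77% of runs. The sensitivity analysis would not run there, yet the nominal 95% interval covers in only about 80% of those runs. With a 75% cut-off it would almost never run at this τ.

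**Exclusion by effect size.** An excluded study contributes more than 1.96² = 3.84 to Q and takes away 1 degree of freedom. Refitting the mean can only lower the remaining Q. So Q minus its degrees of freedom falls by more than 3.84 − 1 = 2.84 per excluded study, whatever the reason for the deviation. In the table at τ = 0.3, mean I² falls from 51% to 7% while coverage moves only from 67% to 73%.

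**Sensitivity to the assumed SEs.** With SEs of 0.15–0.90, τ = 0.3 and a ±2 band, mean I² falls from 32% (uniform SEs) or 44% (log-uniform SEs) to about 6–8%. Coverage goes from 79% to 79% and from 75% to 76% respectively. The size depends on the SE spread; the pattern does not.

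**Egger's test.** Run in every case, with an assumed small-study bias of 1 × SE, it gives p < 0.10 in 58% of runs at τ = 0 and 44% at τ = 0.2. A gate cannot add rejections, only remove them. How many it removes cannot be derived from the protocol.

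**The case against.** Several points on the other side stand.

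- **Publication bias is not checked only when the data look bad.** A reader might infer that from the conditional wording. The funnel and Galbraith plots are unconditional, and only Egger's test is gated. Plot and test will often agree, and readers will see the plot.
- **No study is dropped from the main result.** A reader might infer deletion. The text gives results with and without outliers, so the 18-study estimate remains, and the comparison does show dependence on extreme studies.
- **Spurious outliers among homogeneous studies are not the problem.** A reader might note that 1 − 0.95^18 = 0.60, so some study would often fall outside the band by chance. With τ = 0, however, I² exceeds 50% in only about 1% of runs, so the restricted analysis would almost never take place.
- **Outlier removal does not cause the low coverage.** It is about the same or slightly higher after removal when τ is 0.2 or more. The cause is the fixed-effect model when true effects differ. Under the protocol's own assumption (τ = 0), coverage is 95%.
- **Other safeguards exist.** Section 9.7 promises discussion of departures from the common-effect assumption and of reasons for high heterogeneity, and plans unconditional subgroup analyses.
- **An SAP dated 10 September 2018 exists but is not shown.** It may define the cut-off or add analyses such as trim-and-fill, so their absence from the protocol is no finding.

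These points narrow the concern but do not remove it. The protocol's restriction to high heterogeneity and its condition on Egger's test are stated rules, not details left open. Discussion and subgroup estimates under the same model do not test that model.

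**Conclusion.** The point holds in a limited form. As written, section 9.7 allows a report with moderate heterogeneity to contain no sensitivity analysis of the fixed-effect assumption. When the analysis does run, its selection rule makes the remaining studies look homogeneous without making the interval valid. Egger's test depends on a subjective reading.

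The illustrated size is an untriggered check in about 77% of runs with coverage near 80% (τ = 0.2, SEs 0.1–0.6, cut-off I² 50%). When outliers are excluded, I² falls to single figures with coverage still about 75–79% (τ = 0.3, SEs 0.15–0.90). These figures rest on assumed τ, SEs and cut-offs; the protocol supplies none of them. The loss from gating Egger's test is not quantified. The finding itself rests on the wording and does not need the simulation. It should be corrected before the analysis is run.

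**What to change.** Edit two bullets in section 9.7, and the matching comment in Annex 2 (Section 7):

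1. Delete the sentence "This will be done only in case of high level of heterogeneity observed" and the parenthetical condition attached to Egger's test.
2. State that the following are reported in every case: Egger's test, a random-effects estimate beside the fixed-effect one, leave-one-out results, and a sensitivity analysis by study design or by the Newcastle-Ottawa rating already planned in section 9.8.
3. Keep the Galbraith plot as a diagnostic, and label any with/without-outlier result as exploratory.

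Trim-and-fill, Peters' test and detailed quality exclusions are optional and can sit in the SAP. The cost is a few further calls in the metafor package already named in section 9.7, and slightly more output to report.
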